4.2 Exclusion Criteria

1. Patients with aggressive NK cell leukemia.
2. Patients with primary or secondary central nervous system (CNS) lymphoma.
3. Patients with severe hemophagocytic syndrome at initial diagnosis of ENKTL-NT.
4. Patients with pulmonary great vessel invasion.
5. Previous exposure to any anti-PD-1, anti-PD-L1, or anti-CTLA-4 antibodies.

6. Enrolled in another interventional clinical study, unless only involved in an observational study (non-interventional) or in the follow-up phase of an interventional study.
7. Received any investigational drug within 4 weeks prior to the first dose of study treatment.
8. The last dose of radiation or anti-tumor therapy (chemotherapy, targeted therapy, or tumor embolization) was within 3 weeks prior to receiving the first dose of study treatment; the last dose of nitrosourea or mitomycin C treatment was within 6 weeks prior to receiving the first dose of study treatment.
9. Received immunosuppressants within 4 weeks prior to the first dose of study treatment, excluding local glucocorticoids administered by nasal, inhaled, or other topical routes, or systemic glucocorticoids of physiological doses (no more than 10 mg/day of prednisone or equivalents).
10. Received any live attenuated vaccine within 4 weeks prior to the first dose of study treatment, or is scheduled to receive live attenuated vaccine during the study period.
11. Received major surgery (craniotomy, thoracotomy, or laparotomy) within 4 weeks prior to the first dose of study treatment, or has unhealed wounds, ulcers, or fractures.
12. Active, known, or suspected autoimmune disease (see Appendix 6) or previous medical history of these diseases within 2 years (patients with vitiligo, psoriasis, alopecia, or Graves' disease not requiring systemic treatment, hypothyroidism only requiring thyroid replacement, or type I diabetes only requiring insulin can enroll).
13. Known history of primary immunodeficiency diseases.
14. Known active pulmonary tuberculosis.
15. Known history of allogeneic organ transplantation or allogeneic hematopoietic stem cell transplantation.
16. Known to be allergic to any ingredients of monoclonal antibodies.
17. Uncontrolled concurrent diseases including but not limited to:
 - HIV-infected patients (positive anti-HIV antibody).
 - Active or poorly controlled severe infections.
 - Symptomatic congestive heart failure (NYHA Class III-IV) or symptomatic or poorly controlled arrhythmia.
 - Uncontrolled hypertension (systolic blood pressure \geq 160 mmHg or diastolic blood pressure \geq 100 mmHg) despite of standard treatment.

- Any arterial thromboembolic events occurred within 6 months prior to enrollment, including myocardial infarction, unstable angina, cerebrovascular accident, or transient cerebral ischemic attack.
 - Life-threatening hemorrhagic events or grade 3–4 gastrointestinal /variceal hemorrhage requiring blood transfusion, endoscopy, or surgical treatment within 3 months prior to enrollment.
 - History of deep venous thrombosis, pulmonary embolism, or other serious thromboembolic events within 3 months prior to enrollment (implantable port or catheter-related thrombosis, or superficial venous thrombosis are not considered as serious thromboembolisms).
 - Uncontrolled metabolic disorders, non-malignant organ or systemic diseases, or cancer-related secondary diseases that may lead to higher medical risks and/or survival evaluation uncertainties.
 - Hepatic encephalopathy, hepatorenal syndrome, or cirrhosis with Child-Pugh grade B or C.
 - Bowel obstruction or history of the following diseases: inflammatory bowel disease or extensive bowel resection (partial colectomy or extensive small bowel resection accompanied with chronic diarrhea), Crohn's disease, and ulcerative colitis.
 - Acute or chronic diseases, psychiatric disorders, or laboratory abnormalities that may lead to the following consequences: increased investigational drug-related risks, or interference with interpreting trial results, and considered ineligible for participating in the trial by the investigators.
18. Known acute or chronic active hepatitis B (chronic HBV carriers or inactive HBsAg-positive patients can enroll if the HBV DNA $< 1 \times 10^3$ copies/mL), or acute or chronic active hepatitis C (patients with negative HCV antibody can enroll; HCV RNA test is required for patients with positive HCV antibody, those test negative can enroll).
 19. History of GI perforation and/or fistula without radical treatment within 6 months prior to the enrollment.
 20. Known interstitial lung disease.
 21. Clinically uncontrollable third spacing, such as pleural effusion and ascites that cannot be controlled by drainage or other methods prior to enrollment.

22. History of other primary malignant tumors, excluding:

- History of radical treatment for malignant tumors with no evidence of tumor recurrence for more than 5 years prior to enrollment and with a very low risk of recurrence;
- Adequately treated nonmelanoma skin cancer or lentigo maligna with no signs of disease recurrence;
- Adequately treated carcinoma in situ with no signs of disease recurrence.

23. Pregnant or breastfeeding female patients.

4.3 Restrictions During the Study

For women of childbearing potential who are sexually active with male partners who have not undergone surgical sterilization, the subjects must use 1 acceptable and effective methods of contraception (see Table 2) starting from the screening, and agree to continue these measures during the 90 days since the last dose of study treatment. Besides, the subjects shall discuss with a responsible physician about the discontinuation of contraception after this time point. Periodic abstinence, calendar-based method, and withdrawal method are not the acceptable forms of contraception.

Women of childbearing potential is defined as any female who has not undergone surgical sterilization (bilateral tubal ligation, bilateral oophorectomy, or hysterectomy) or is not postmenopausal (defined as 12 months of amenorrhea without alternative medical causes).

Menopause is defined as 12 months of amenorrhea of a woman without any other medical reasons. Age requirement are as follows:

- Females ≥ 50 years old who have at least 12 months of amenorrhea after stopping hormone replacement therapy, and luteinizing hormone and follicle stimulating hormone levels within the postmenopausal range, are considered menopausal;
- Females < 50 years old who have at least 12 months of amenorrhea after stopping hormone replacement therapy, radiation-induced ovariectomy and the time from the last menorrhoea > 1 year, chemotherapy-induced amenorrhea and the time from the last menorrhoea > 1 year, or surgical sterilization (bilateral ovariectomy or hysterectomy), are considered menopausal.

Table 2. Effective methods of contraception (one of the followings must be used)

Barrier Method	Intrauterine Devices (IUDs)	Hormonal Methods
Male condom with spermicide	Copper-T IUD	Implant

Barrier Method	Intrauterine Devices (IUDs)	Hormonal Methods
Cervical cap with spermicide	Progesterone-T IUD ^a	Hormonal injection
Diaphragm with spermicide	Levonorgestrel-releasing intrauterine system (e.g. Mirena [®]) ^a	Combined oral contraceptive pill Low-dose oral contraceptive pill Contraceptive patch

^aAlso considered as a hormonal method.

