4.1 Inclusion Criteria

1. Histologically confirmed ENKL-NT.
2. Relapsed or refractory ENKTL-NT. Being relapsed is defined as presence of new lesions at the primary location or other sites after achieving CR; being refractory is defined as any one of the followings: PD after 2 treatment cycles, PR not achieved after 4 treatment cycles, or

CR not achieved after 6 treatment cycles. Patients who do not response or patients with relapsed disease or PD after autologous stem cell transplantation can enroll.

3. Must have been treated with asparaginase-based regimen (radiotherapy must be performed for stage I/II disease).
4. Long axis of a lesion > 15 mm or ¹⁸FDG-PET uptake by lesion.
5. Eastern Cooperative Oncology Group Performance Status (ECOG PS) scores of 0–2.
6. Signed the ICFs and able to comply with the scheduled follow-up visits and related procedures required in the protocol.
7. Between the ages of ≥ 18 to ≤ 70 years.
8. Life expectancy ≥ 12 weeks.
9. Patients (female patients at childbearing age or male patients whose partners are at childbearing age) must take effective contraceptive measures during the entire course of the trial and within 90 days since the last dose of treatment (see Section 4.3).
10. Adequate organs and bone marrow functions, as defined below:
 - Count of whole blood cells: absolute neutrophil count (ANC) $\geq 1.0 \times 10^9/L$, platelets (PLTs) count $\geq 50 \times 10^9/L$, hemoglobin (HGB) ≥ 8.0 g/L; granulocyte colony-stimulating factor, PLT, or red blood cell (RBC) transfusion has not been performed within 7 days prior to the test.
 - Hepatic function: total bilirubin (TBIL) $\leq 1.5 \times$ upper limit of normal (ULN), alanine aminotransferase (ALT) and aspartate aminotransferase (AST) $\leq 2.5 \times$ ULN.
 - Renal function: serum creatinine (Cr) $\leq 1.5 \times$ ULN.
 - Thyroid function: normal thyroid stimulating hormone (TSH) at baseline, or abnormal TSH at baseline with normal T3/T4 and no symptoms.

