6.4.6 Pregnancy test

Urine or serum β human chorionic gonadotropin (β -HCG) pregnancy test must be performed in women of childbearing potential (refer to Section 4.3 for definition) within 3 days prior to the first dose of study treatment. If the result of urine β -HCG is positive or inconclusive, then serum β -hCG pregnancy test shall be performed. The conclusion shall be based on the serum pregnancy test. If the β -hCG result is positive, the subject is not eligible or must discontinue participating in the study. A repeated test shall be performed if pregnancy is suspected during the study.

6.4.7 Other safety examinations include the followings:

- Hepatitis B panel (HBsAg, HBsAb, HBcAb, HBeAg, and HBeAb).
- HIV antibody, HCV antibody (if the result shows HCV antibody positive, then HCV RNA test shall be further conducted).
- Thyroid function: T3, T4, TSH, FT3, and FT4. T3, T4, FT3, FT4, and TSH shall be tested during screening and prior to the administration of IBI308 from Cycle 2 onwards.

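### Protocol 4.3 asks for weaker proof of menopause under 50 than at 50 or over, so a younger woman with chemotherapy-induced amenorrhea can fall outside the scheduled pregnancy tests and the contraception rule

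*Protocol*

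**What the plan says.** Protocol 4.3 applies its contraception rule to women of childbearing potential, from screening until 90 days after the last dose. It defines such a woman as one who has not been surgically sterilised "or is not postmenopausal (defined as 12 months of amenorrhea without alternative medical causes". A general sentence follows: "Menopause is defined as 12 months of amenorrhea of a woman without any other medical reasons". Two age bullets then say who counts as menopausal.

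- **50 or over:** 12 months of amenorrhea after stopping HRT, and "luteinizing hormone and follicle stimulating hormone levels within the postmenopausal range, are considered menopausal".
- **Under 50:** any one of four routes. These are "Females < 50 years old who have at least 12 months of amenorrhea after stopping hormone replacement therapy"; ovariectomy by radiation, with more than 1 year since the last period; "chemotherapy-induced amenorrhea and the time from the last menorrhoea > 1 year"; or surgical removal of the ovaries or uterus. None of the four mentions LH or FSH.

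Other sections rely on this classification. Protocol 6.4.6 says that a "pregnancy test must be performed in women of childbearing potential (refer to Section 4.3 for definition) within 3 days prior to the first dose". Note 7 to Table 1, repeated in SAP Appendix 1, limits both scheduled tests (before the first dose and at the end-of-treatment visit) to the same group. Section 7.6 states an embryotoxicity risk for the drug class and ties contraception to childbearing potential. Inclusion criterion 9 uses a different term: "Patients (female patients at childbearing age or male patients whose partners are at childbearing age) must take effective contraceptive measures". It then refers the reader back to 4.3.

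**The concern.** The standard runs the wrong way. The protocol does not accept 12 months of amenorrhea off HRT as sufficient at 50 or over, yet accepts it alone in a younger woman. It also accepts amenorrhea with a named treatment cause, although its own general definition excludes such causes.

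The case is foreseeable here. Eligible ages are 18 to 70 (criterion 7), and every subject must already have had an asparaginase-based regimen (criterion 3). Treatment can last 24 months. At stake are the protection of subjects and uniform practice across sites. No efficacy result depends on it.

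**Working it through.** The plan gives no figure to reproduce, so the check compares the texts and then works through the definition.

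**1. Proof required of a non-sterilised woman (4.3, age bullets)**

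| Age and route | Amenorrhea | LH/FSH | Fits the general definition? |
|---|---|---|---|
| 50 or over, off HRT | 12 months | required | yes, if no other cause |
| Under 50, off HRT | 12 months | not required | yes, if no other cause |
| Under 50, after chemotherapy | more than 1 year | not required | no, a medical cause is named |

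The two HRT rows differ only in age and in the hormone check, and the younger woman has the lighter requirement. The chemotherapy row has that weakness and also departs from the general sentence.

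**2. What follows from the classification.** Take a non-sterilised woman under 50 with chemotherapy-induced amenorrhea of more than 1 year.

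- If the age bullets govern, she is menopausal and so not of childbearing potential. Neither of the two note 7 tests applies, and neither does the 4.3 contraception rule.
- If the general sentence overrides the bullets, chemotherapy is another medical reason. She stays of childbearing potential, and both tests and the rule apply.

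No sentence says which governs. A woman in the HRT route with no other cause is menopausal under either, so only the missing hormone check is at issue for her.

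**3. The connective in the childbearing-potential definition.** Let S = surgically sterilised and M = postmenopausal.

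| S | M | Literal: not S *or* not M | Neither/nor: not S *and* not M |
|---|---|---|---|
| no | no | yes | yes |
| no | yes | yes | no |
| yes | no | yes | no |
| yes | yes | no | no |

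The literal form captures 3 of the 4 combinations and the neither/nor form 1 of 4. Taken literally, a woman of 55 with postmenopausal LH/FSH and no sterilisation is of childbearing potential, and so is a menstruating woman with a tubal ligation. The age bullets could then exempt no non-sterilised woman. Neither/nor is plainly meant, but it is not what is written.

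**4. Hormone results.** Neither Table 1 nor sections 6.4.1 and 6.4.7 schedule LH or FSH, even for women aged 50 or over. Any remedy therefore needs a default for women without a result.

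**The case against.** The strongest reply is that 4.3 is not hard to apply. A general sentence followed by specific age rules is ordinary drafting, and letting the age rules govern is the only approach that gives every bullet effect. This is persuasive, and it rules out the literal *or* as a serious option. It does not remove the problem, because this natural reading is the one that exempts the younger woman.

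A second reply is that other provisions still protect her. That is partly right:

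- Criterion 9 speaks of childbearing age, which she may well meet, although it refers back to 4.3.
- Exclusion criterion 23 bars pregnant women, but does not itself order a test.
- Sections 6.2.1 and 6.2.4 list the pregnancy test at screening and at end of treatment without limiting it to women of childbearing potential. Note 7 limits both tests, and 6.4.6 limits the first.
- Section 6.4.6 adds: "A repeated test shall be performed if pregnancy is suspected during the study".
- Section 7.6 requires withdrawal of a pregnant subject and a report within 24 hours.

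A reader might therefore infer too much in saying that the plan leaves these women unprotected or lets pregnant women be dosed. The documents do not support that.

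A third reply is that radiation and surgery are also medical reasons, so singling out chemotherapy is selective. As to the general definition, this stands. For the remedy there is a textual ground for a difference: the surgical route is already sterilisation, and the radiation route is described as loss of the ovaries rather than as absent periods alone. A reader might also want to argue that chemotherapy-induced amenorrhea can reverse. The documents do not say so, and the point does not need it. It rests on the stricter proof that the protocol itself sets at 50 or over.

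Finally, the Summary of Amendment reports a pause in enrolment at 28 patients and does not say whether it resumed. If it did not, the test before the first dose is past for everyone, and the benefit falls on women still treated or recently treated.

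**Conclusion.** The point holds as a modest matter of subject protection and clarity, worth considering. Section 4.3 sets the weaker proof of menopause for the younger group, and its chemotherapy route conflicts with its general definition. The loose *or* is a separate drafting fault.

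For each affected woman, what turns on it is two scheduled pregnancy tests, and contraception during up to 24 months of treatment and for 90 days afterwards. The documents do not give the number of such women; it may be zero, and no estimate is offered. The conclusion that she is exempt assumes that sites let the age bullets govern and follow note 7 and 6.4.6 rather than the unrestricted visit lists.

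A reader might infer that the section is unworkable, or that trial results are at risk. Neither follows: one reading is clearly the natural one, and ORR, power, alpha and the planned analyses do not depend on this classification.

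**What to change.** Change wording in 4.3 only.

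1. Define a woman of childbearing potential as one who is *neither surgically sterilised nor postmenopausal under the age rules below*, and state that the age rules govern over the general sentence.
2. For non-sterilised women under 50 in the HRT or chemotherapy route, require documented LH and FSH in the postmenopausal range before classing them as menopausal. Without such results, treat them as of childbearing potential. Leave the surgical and radiation routes as they are.
3. Apply the existing pregnancy test to affected women still on treatment. Apply the existing contraception rule to those on treatment or within 90 days of the last dose.

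Because the default covers women without hormone results, no new row in Table 1 and no scheduled hormone sample is needed. The cost is a few extra urine tests, contraception for a small and possibly zero number of women, and submission of the amendment to the ethics committee for approval or filing under Protocol 11.3.

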4.4 Treatment Discontinuation/Withdrawal from the study

Subjects should discontinue treatment/withdrawal from the study in any of the following circumstances:

1. Subjects do not meet the inclusion/exclusion criteria, and are deemed unsuitable to continue in this study by the sponsor and investigator.
2. Subjects seriously violate the study protocol, and deemed unsuitable to continue in this study by the sponsor and investigator.
3. Subjects are enrolled in another clinical trial that is considered scientifically or medically incompatible with this study.
4. Subjects are lost to follow-up (study site personnel shall regain contact with the subjects to determine the cause of loss to follow-up and reschedule study visits if possible. The date and method of contact shall be documented in the study documents).
5. Decided by the investigator
 - Subjects should discontinue the treatment or withdraw from the study based on the safety and benefits of the subjects.
 - If the subjects require treatment with another drug for any reason, and the drug has been demonstrated to be effective for the indication of this study, then the subject shall withdraw from this study prior to starting the new drug.
 - PD is developed or the investigator believes that continuing with study treatment is not appropriate.
 - A life-threatening event that is treatment-related occurred, regardless of the severity of the event.
 - The investigational drug shall be discontinued due to toxicities (see Section 5.4).
6. Subjects or their representatives (such as parents or legal guardians) requests to withdrawal from the study or discontinue the investigational drug (subjects may be

eligible for long-term follow-up if he/she withdraws ICF for treatment but not for follow-up).

7. The sponsor may terminate the study or discontinue a subject from participating in the study due to medical, safety, regulatory, or other reasons related to the applicable laws, regulations, and Good Clinical Practice (GCP).
8. Subjects who delay the treatment for 6 weeks due to adverse reactions shall withdraw from the study.
9. Subjects may withdraw from the study if the investigator believes that the local lesions should also be treated with radiation or other therapies after the subject reaches the primary endpoint.

The reasons and dates of discontinuation for all the subjects shall be documented. Subjects who discontinue the treatment shall undergo other study procedures as specified in the schedule of visits.

5 Investigational Drug and Other Treatments

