c: For grade 4 laboratory abnormalities, the event shall be determined based on clinical signs/symptoms and the clinical judgment of the investigator.

Investigational drug is allowed to be interrupted for up to 6 weeks. If the symptoms do not resolve within 6 weeks and treatment cannot be resumed, the subject must permanently discontinue IBI308 treatment and enter the follow-up phase of the study. Except for the following two cases:

- IBI308 interruption > 6 weeks due to glucocorticoid reduction for irAEs: Consult the sponsor's medical manager prior to resuming IBI308. Tumor imaging evaluation for efficacy shall not be affected by treatment interruption and will be performed as scheduled.
- IBI308 interruption > 6 weeks due to AEs possibly related or unrelated to IBI308: Consult the sponsor's medical manager prior to resuming IBI308. Tumor imaging evaluation for efficacy shall not be affected by treatment interruption and will be performed as scheduled.

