6.3 Imaging Evaluation

Baseline evaluation is conducted within 28 days prior to the first dose of the study treatment. The investigator can evaluate the imaging results within 28 days prior to the enrollment.

PET-CT and contrast-enhanced CT will be used (MRI will be performed for subjects allergic to CT contrast media). PET-CT shall be performed at baseline, week 6 (± 7 days), week 15 (± 7 days), and week 24 (± 7 days). PET-CT evaluation shall be performed at the end of treatment for subjects who discontinue the treatment prematurely prior to week 24 (unless the previous PET-CT scan is done within the past month). Contrast-enhanced CT shall be performed at baseline, week 24 (± 7 days), every 12 weeks (± 14 days) after 24 weeks, and every 24 weeks (± 14 days) after 48 weeks initiation of new anti-tumor therapy, PD, withdrawal of ICF, or death. Unplanned PET-CT and contrast-enhanced CT shall be added to evaluate the efficacy when investigators deem appropriate, if the subjects agree. The examinations will be taken at sponsor's expense. First PD shall be confirmed after 4–6 weeks. For subject who discontinue the treatment for reasons other

than PD, tumor imaging evaluation shall be continued according to the study protocol until initiation of new anti-tumor therapy, PD, withdrawal of ICF, or death.

Imaging data shall be copied or saved according to the requirements of the sponsor.

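### Protocol 4.4 item 8 takes a subject out of the study after a 6-week toxicity delay, while 5.3.2 and 6.2.5 to 6.3 keep that subject in follow-up; a site that follows item 8 creates avoidable, possibly informative, dropout.

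*Protocol*

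**What the plan says.** Two protocol sections address a dosing delay of about 6 weeks.

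- **Section 4.4, item 8:** "Subjects who delay the treatment for 6 weeks due to adverse reactions shall withdraw from the study". No exception is attached.
- **Section 5.3.2, after Table 3:** "Investigational drug is allowed to be interrupted for up to 6 weeks". If symptoms have not resolved by then and dosing cannot resume, "the subject must permanently discontinue IBI308 treatment and enter the follow-up phase of the study". Two exceptions follow: "IBI308 interruption > 6 weeks due to glucocorticoid reduction for irAEs" and "IBI308 interruption > 6 weeks due to AEs possibly related or unrelated to IBI308". Each carries the condition "Consult the sponsor's medical manager prior to resuming IBI308", and each says that efficacy imaging stays on schedule.

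Other passages describe what happens once treatment stops.

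- **4.4, closing sentence:** "Subjects who discontinue the treatment shall undergo other study procedures as specified in the schedule of visits".
- **6.2.5:** subjects whose drug-related AE led to discontinuation are followed until resolution to grade 0 or 1, stable symptoms, withdrawal of consent or new anti-tumor therapy.
- **6.2.6:** survival contacts every 60 days until death or end of study.
- **6.3:** after a stop for a reason other than PD, "tumor imaging evaluation shall be continued according to the study protocol until" new anti-tumor therapy, PD, withdrawal of consent or death.

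SAP 5.5.2 censors PFS and DoR at the last imaging assessment. Protocol 8.4.3 defines OS as time from first dose to death, and neither document adds a censoring rule for it.

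**The concern.** Item 8 orders the subject out of the study; 5.3.2 orders the subject off the drug. These have different consequences for the data. Under 5.3.2, progression and death are still observed. Under item 8, observation ends because of toxicity, and toxicity may be related to prognosis. Kaplan-Meier estimation treats such a subject as having the same future risk as those who remain, and the SAP names no sensitivity analysis for withdrawal after toxicity.

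The endpoints at stake are PFS, DoR and OS. In a trial of this size a few subjects can move a landmark rate visibly. Sites also have no text telling them which section prevails when a delay passes 6 weeks.

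**Working it through.** **Step 1. Can both rules be obeyed?** Take a subject whose drug is held for more than 6 weeks while glucocorticoids are tapered for an immune-related AE. Protocol 5.4 treats such an event as related to IBI308, so it is an adverse reaction under item 8.

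| | 4.4 item 8 | 5.3.2 |
|---|---|---|
| Delay of exactly 6 weeks | leaves the study | still permitted |
| Over 6 weeks, steroid taper for an irAE | leaves the study | may resume after consultation |
| Over 6 weeks, no exception applies | leaves the study | stops drug, stays in follow-up |

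No row satisfies both sections. The taper case is foreseeable: for renal events, Appendix 7 has glucocorticoids tapered over at least 1 month.

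**Step 2. How wide is the second exception?** Table 5 grades causality as definitely related, probably related, probably unrelated, definitely unrelated or unable to determine. The exception's term, possibly related, is not among them, so its scope cannot be settled from the text.

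**Step 3. When can item 8 act?** The second dose is due on Day 22 (Table 1). Counting the delay from that due date (an assumption, since the protocol does not say where counting starts), 22 + 42 = Day 64. The week-6 PET-CT, with its ±7 days, falls before that.

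**Step 4. Size.** The plan gives no figure here: no count of such withdrawals and no dropout allowance. Inputs:

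- n = 28, the number enrolled when enrollment was paused (protocol, Summary of Amendment), for illustration only.
- d = 2 to 4 subjects withdrawn under item 8: assumed.
- True 6-month PFS of 50%, so 14 of 28 progress or die by 6 months: assumed.

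Let k be the number of events among the other subjects before the d are censored.

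- All d would have had an event by 6 months: KM = [(28 − k)/28] × [14/(28 − k − d)].
- None of the d would: KM = [(28 − k)/28] × [(14 − d)/(28 − k − d)].

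Censoring right after the first dose (k = 0):

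- d = 2: 14/26 = 53.8% or 12/26 = 46.2%, so +3.8 or −3.8 points.
- d = 4: 14/24 = 58.3% or 10/24 = 41.7%, so +8.3 or −8.3 points.

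Censoring as late as possible:

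- None would have had an event (k = 14): KM = (14/28) × 1 = 50%, no error.
- All would have (k = 14 − d): KM = (14 + d)/28, which is 16/28 = 57.1% for d = 2 and 18/28 = 64.3% for d = 4, so +7.1 and +14.3 points.

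Later censoring therefore removes the downward error and enlarges the upward one towards d/28.

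**The case against.** The strongest reply is that the protocol's intention is clear from everything around item 8. The closing sentence of 4.4 and sections 5.3.2, 6.2.5, 6.2.6 and 6.3 all continue follow-up after a stop, and a 6-week delay is not among the reasons in 6.3 for ending imaging. Data are lost only if a site follows one sentence against all of these. That stands as a limit on likelihood. It does not cure item 8: the closing sentence covers subjects who discontinue treatment, whereas item 8 orders withdrawal from the study. Item 6 of the same section separates leaving treatment from leaving follow-up, so the distinction was available.

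The group may also be small. Table 3 already requires permanent discontinuation for many grade 3 or 4 events, and those stops do not pass through item 8. This stands too; no count is given.

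The argument that the effect is smaller in practice, because item 8 acts only after the week-6 scan, holds for the downward error alone (Step 4).

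Four stronger readings should be resisted.

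- A reader might infer that subjects are censored at the toxicity. PFS and DoR are censored at the last imaging date, and SAP 4.3 sends subjects with missing post-treatment tumor evaluations to a pre-lock review of the censoring time.
- A reader might infer that OS is censored by rule at withdrawal. No OS censoring rule exists in either document.
- A reader might infer that the exceptions in 5.3.2 cover almost every delay. Both need consultation first, definitely or probably related AEs without a steroid taper are not listed, and the second exception's scope is undefined.
- A reader might take 7 to 14 points as the expected bias. It is the best-to-worst range for 2 to 4 unknown outcomes (2/28 and 4/28). As an upward error it is reached only if every withdrawn subject would have progressed or died by 6 months and is censored after all other events by then.

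**Conclusion.** The contradiction is in the current text and should be corrected. Followed as written, item 8 ends observation for a toxicity-related reason, which exposes PFS and DoR to informative censoring and leaves the handling of OS undefined. Whether that happens depends on which section sites follow, and the documents do not show that it has.

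With 2 to 4 of 28 subjects affected and a true 6-month PFS of 50%, both assumed, the Kaplan-Meier error is about 4 to 8 points in either direction for censoring right after the first dose. Since item 8 acts later, the downward error would be smaller, while the upward error could be larger, up to the 7 to 14 point extreme. No direction is established. The sample size of 43 is not affected.

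**What to change.** Reconcile 4.4 item 8 with 5.3.2 and its exceptions, including the status of a delay of exactly 6 weeks, and express the second exception in Table 5 categories. State in 4.4 that stopping study drug because of a delay is not withdrawal from the study, so that imaging (6.3), safety follow-up (6.2.5) and survival follow-up (6.2.6) continue unless consent for follow-up is withdrawn or another stop stated in those sections applies. Which delay rule governs resumption is for the sponsor to decide.

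In the SAP, add a censoring rule for OS.

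The cost is wording in the protocol and one line in the SAP. The visits already exist in Table 1.
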